3.2 Secondary Efficacy Endpoints

- Absolute change in the percentage of LFC (assessed by MRI-PDFF) from baseline to Week 36 (V8-EoT)
- Response defined as an absolute reduction in LFC $\geq 5\%$ from baseline to Week 36 (V8-EoT)
- Response defined as a relative reduction in LFC $\geq 30\%$ from baseline to Week 36 (V8-EoT)
- Response defined as a relative reduction in LFC $\geq 50\%$ from baseline to Week 36 (V8-EoT)
- Response defined as a LFC value at Week 36 (V8-EoT) that is normalized, i.e. $\leq 5\%$
- Change in the following parameters from baseline to Week 36 (V8-EoT):
 - Liver enzymes: Alanine aminotransferase (ALT), Aspartate aminotransferase (AST), gamma-glutamyl transferase (GGT), alkaline phosphatase (ALP)
 - Percentage of responders as defined by the percentage of patient with normalization of liver enzymes in the subset of patients with increased baseline value
 - Measured glycemic parameters: Fasting plasma glucose (FPG), Glycated hemoglobin (HbA1c), serum insulin, C-peptide
 - Insulin resistance indexes: Homeostasis model assessment of insulin resistance (HOMA-IR), Quantitative insulin sensitivity check index (QUICKI), Homeostasis model assessment of β -cell function (HOMA- β) and Adipose tissue insulin resistance (Adipo-IR)

Exploratory endpoints

Change from baseline in the following parameters at Week 36 (V8-EoT):

- Adiponectin
- Lipids: total cholesterol, low-density lipoprotein cholesterol (LDL-c), high-density lipoprotein cholesterol (HDL-c), triglycerides, free fatty acids (FFA)
- Biomarker of inflammation: High-sensitivity C-reactive protein (hsCRP)
- Biomarkers of fibrosis: N-terminal type III collagen propeptide (pro-C3), NAFLD Fibrosis score (NFS) and Fibrosis 4 (FIB-4) score and Enhanced Liver Fibrosis (ELF) score
- Histological change in liver biopsy:
 - Change in NAFLD Activity Score (NAS), in each component of NAS (steatosis, ballooning and inflammation) and in NASH CRN fibrosis score
 - Improvement in each component of NAS (steatosis, lobular inflammation and hepatocellular ballooning) by ≥ 1 point without worsening of fibrosis
 - Improvement in NAS by ≥ 2 points without worsening of fibrosis
 - Improvement in NASH CRN fibrosis score by ≥ 1 point

Statistical Analysis Plan

Sponsor Name: Poxel
Sponsor Protocol ID: PXL065-003

- NASH resolution (NAS score of 0-1 for inflammation, 0 for ballooning, and any value for steatosis)
- NASH resolution (NAS score of 0-1 for inflammation, 0 for ballooning, and any value for steatosis) with improvement in NASH CRN fibrosis score by ≥ 1 point
- NASH resolution (NAS score of 0-1 for inflammation, 0 for ballooning, and any value for steatosis) with no worsening in NASH CRN fibrosis score
- NASH resolution (NAS score of 0-1 for inflammation, 0 for ballooning, and any value for steatosis) and improvement in NAS by ≥ 2 points with no worsening in NASH CRN fibrosis score
- [Corporate confidential information](#)

3.3 Safety Variables

Safety and tolerability will be assessed on the following parameters:

- Adverse events (AEs)
- Physical examination
- Weight, waist and hip circumferences, and BMI
- Vital signs: systolic blood pressure (SBP), diastolic blood pressure (DBP), heart rate (HR)
- Pitting edema assessment
- 12-lead electrocardiogram (ECG)
- Bone mineral density in postmenopausal women
- Biological parameters: biochemistry, hematology, coagulation
- Estimated Glomerular Filtration Rate (eGFR) (Chronic Kidney Disease – Epidemiology Collaboration [CKD-EPI] formula)
- Urinalysis

4. Pharmacokinetic Variables

Pharmacokinetics (PK) analysis will be done separately and consequently not reported in this SAP.

5. Analysis Populations

The analysis populations have been adapted due to data integrity being compromised at site 065-S:

[Corporate confidential information](#)

Statistical Analysis Plan

Sponsor Name: Poxel
Sponsor Protocol ID: PXL065-003

Corporate confidential information

As a consequence, patients from site 065-S₁ are excluded from principal analysis. Primary and some secondary endpoints will be analyzed including patients from site 065-S₁ in a sensitivity analysis. Details of tables which will include site 065-S₁ will be described in each dedicated part. In addition, site 065-S₁ patients that did not complete the study will have treatment exposure end date coded as 23rd December 2021, corresponding with the site early termination date. This change will impact some derivations e.g., treatment-emergent AEs, duration of exposure, etc. Details of the quality issue and data handling at site 065-S₁ are available in the note to file.

5.1 Screened Set

All patients except patients from site 065-S₁, who were screened for inclusion into the study will be included in the screened set. Patients who are rescreened will be considered once utilizing their most recent subject identifier.

5.2 Screened Set with Site 065-S₁

All patients who were screened for inclusion into the study will be included in the screened set with site 065-S₁. Patients who are rescreened will be considered once utilizing their most recent subject identifier.

5.3 Randomized Set (RS)

All patients except patients from site 065-S₁, considered as-randomized regardless of the treatment actually received.

5.4 Randomized Set with Site 065-S₁ (RS-w-065-S₁)

All patients including patients from site 065-S₁, considered as-randomized regardless of the treatment actually received.

5.5 Safety Set (SS)

All randomized patients except patients from site 065-S₁, having received at least one dose of the IMP (either PXL065 or placebo) and considered as-treated will be included in the Safety set. The Safety set will be considered as the primary set for safety and tolerability analyses. Safety patients are analyzed according to their actual treatment received.

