#### 9.4.2 Safety Set

The Safety Set (SS) comprises all randomized patients having received at least one dose of the IMP (either PXL065 or placebo) and considered as-treated. Safety and tolerability will be analyzed on the safety set.

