5.6 Safety Set with Site 065-S₁ (SS-w-065-S₁)

All randomized patients including patients from site 065-S₁ having received at least one dose of the IMP (either PXL065 or placebo) and considered as-treated will be included in the Safety set with site 065-S₁. The Safety set with site 065-S₁ will be considered as the secondary set for some safety and tolerability analyses. Safety patients are analyzed according to their actual treatment received.

Statistical Analysis Plan

Sponsor Name: Poxel
Sponsor Protocol ID: PXL065-003

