7.7 Safety

7.7.1 Extent of Exposure

Duration of exposure will be listed for the Safety set with site 065-S and summarized using descriptive statistics for each treatment group for the Safety set, based on dosing records of the IMP medication on the eCRF. Duration of exposure will be calculated as follows:

Date of Last Study Drug Administration – Date of First Study Drug Administration + 1.

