7.7.8 Pitting Edema

Shift tables from baseline will be presented at each post-baseline visit showing the number of patients per treatment group with each populated grade for the Safety set.

A listing will also be provided for the Safety set with site 065-S .

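### Several safety summaries, including edema grade, hypoglycemia class, bone density and exposure, have no table that includes the dosed patients of site 065-S; a few repeat tables would close the gap

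*SAP*

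**What the plan says.** Protocol 9.4.2 states that the Safety Set "comprises all randomized patients having received at least one dose of the IMP", analyzed as treated, and protocol 9.5.3 bases the safety analysis on that set.

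SAP section 5 says that data integrity was compromised at one site and that its patients "are excluded from principal analysis". The detail is blacked out and a note to file is cited. SAP 5.5 accordingly starts the Safety Set from "All randomized patients except patients from site 065-S" and adds: "The Safety set will be considered as the primary set for safety and tolerability analyses". SAP 5.6 defines a second set that includes the site, which "will be considered as the secondary set for some safety and tolerability analyses".

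The individual sections of SAP 7.7 then name the set for each table. Exposure (7.7.1) is "summarized using descriptive statistics for each treatment group for the Safety set". The pitting-edema shift tables (7.7.8) are presented "showing the number of patients per treatment group with each populated grade for the Safety set". In both cases only the listing includes the site. SAP 6.3 gives the general rule: site patients go into every listing but only into selected tables.

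**The concern.** Doubt about a site's data is a sound reason to keep it out of the main efficacy estimate. For safety the position differs: as far as the plan shows, these patients took study drug, and what happened to them belongs in the description of harm. The protocol's background section names weight gain, fluid retention and bone loss as effects linked to PPARγ activation, and pitting edema and fracture are AESIs. With about 30 patients planned per arm, one or two cases can change how an arm looks. If graded edema, hypoglycemia class or bone change at this site can be found only by reading listings, the tabulated picture in those areas does not cover all dosed patients. The repeated TEAE tables also have no with-site exposure summary beside them.

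**Working it through.** **1. Which tables include the site**

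| Safety output | SAP section | Table with the site? |
|---|---|---|
| TEAE overview, with rows for the five AESI types and for TEAEs leading to discontinuation | 7.7.2 | Yes |
| TEAEs, related TEAEs and TESAEs by SOC/PT | 7.7.2 | Yes |
| Weight summary and MMRM | 7.7.5 | Yes |
| ALT, AST, FPG, HbA1c | 7.6.2.3 | Yes, on ITTS-w-065-S |
| Liver-limit elevations | 7.7.3.1 | The only output named is a listing, which includes the site |
| Exposure | 7.7.1 | No |
| AESIs by SOC/PT; discontinuation TEAEs by SOC/PT | 7.7.2 | No |
| Hypoglycemia by class | 7.7.2.1 | No |
| Other laboratory summaries; eGFR and CKD-stage shift | 7.7.3 | No |
| BMD change | 7.7.4 | No |
| ECG | 7.7.6 | No |
| Pitting-edema grade shift | 7.7.8 | No |

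ITTS-w-065-S also requires at least one dose, so it holds the same patients as the Safety Set with the site, grouped as randomized instead of as treated.

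**2. Whether the repeated AE tables stand in for the missing ones**

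- Edema grade is recorded at every visit (protocol 8.3.2). An edema AE enters the repeated SOC/PT table, but the change in grade does not.
- SAP 7.7.2.1 codes every hypoglycemic event to a single preferred term, so the repeated table counts events but cannot separate severe from asymptomatic ones.
- BMD and laboratory changes reach the AE tables only if judged clinically significant or otherwise reportable under protocol 8.3.6, 8.3.7 and 8.3.8.1.3. The distribution of change does not.
- SAP section 5 assigns 23 December 2021 as the exposure end date for site patients who did not complete, and says this affects TEAE status and exposure duration. TEAE status runs to 7 days after discontinuation (7.7.2). The repeated TEAE tables rest partly on that date, with no with-site exposure table beside them.

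**3. Size**

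The plan gives no figure to reproduce, because the number of site patients is not stated. Assume *m* dosed site patients, from 6 to 24 of the planned 120 (6/120 = 5%, 24/120 = 20%), and a per-patient event risk *p*. The chance that at least one affected patient is among those omitted from a given table is 1 − (1 − *p*)^*m*.

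| *m* | *p* = 2% | *p* = 5% | *p* = 10% |
|---|---|---|---|
| 6 | 11.4% | 26.5% | 46.9% |
| 12 | 21.5% | 46.0% | 71.8% |
| 24 | 38.4% | 70.8% | 92.0% |

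For *p* = 2%: 1 − 0.98^6 = 0.114 and 1 − 0.98^24 = 0.384.

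The chance that every affected patient in the trial is at this site is much smaller, because the remaining patients must also be event-free: 0.114 × 0.98^114 = 0.011 for 6 patients and 0.384 × 0.98^96 = 0.055 for 24.

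**The case against.** The strongest reply is that the plan already shows most of what matters. The repeated overview covers heart failure, pitting edema, bladder cancer, fracture and DILI, as well as SAEs, deaths and discontinuations. Any edema, fracture or hypoglycemia reported as a TEAE is in the repeated SOC/PT table. Disposition is also tabulated with the site (SAP 7.2), and the exclusion is openly disclosed. This stands, and it rules out several stronger readings.

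- A reader might infer that harms at the site are hidden. They are not: they are in every listing, and adverse events are also in the repeated tables.
- A reader might infer that no laboratory result is tabulated with the site. SAP 7.6.2.3 repeats ALT, AST, FPG and HbA1c.
- A reader might infer that the effect of the exclusion cannot be checked. For the AE overview, the three SOC/PT tables and weight, it can.
- A reader might take 11% to 38% as the chance that an event occurs only among the omitted patients. That chance is about 1% to 5.5%.

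The second reply is that the reason for exclusion is blacked out, so the site's measurements may be unreliable, and a with-site exposure table would rest partly on an administrative date. This stands as a caution and calls for a footnote. It does not justify having no table, because the SAP already uses the site's data elsewhere: the primary endpoint is re-analyzed with it (7.6.1.3), and the Per-Protocol Set is drawn from the set that includes it (5.9). The visible text gives no reason for treating the missing safety tables differently; the note to file may contain one.

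**Conclusion.** The point holds as one of completeness. The primary Safety Set is narrower than the protocol's, and a defined group of safety summaries has no version covering all dosed patients: exposure, AESIs and discontinuation TEAEs by SOC/PT, hypoglycemia by class, BMD, edema grade shift, ECG, and eGFR and other laboratory summaries. What is lost from the tables is grade, class and measured change, together with an exposure summary to match the repeated TEAE tables. The reported events themselves are not lost.

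The size cannot be fixed from the documents. At 2% risk, the chance that at least one affected patient is omitted from a given table is 11% with 6 site patients and 38% with 24. Both the patient numbers and the risk are assumptions. The conclusion does not depend on them, because it follows from the set named for each table.

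**What to change.** Keep the SAP's primary Safety Set. As footnoted sensitivity tables on the Safety Set with site 065-S, repeat:

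- exposure (7.7.1), with a note on the assigned end date of 23 December 2021 for site non-completers;
- AESIs by SOC/PT and TEAEs leading to discontinuation by SOC/PT (7.7.2);
- hypoglycemia by class (7.7.2.1);
- BMD change (7.7.4);
- the pitting-edema grade shift (7.7.8).

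ECG, eGFR and the remaining laboratory summaries can stay as listings if the SAP says so and gives the reason. No liver-limit repeat is needed, since that listing already includes the site.

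The cost is about six extra tables from programs that already have to be written. The downside is that some values come from a site with a known data-integrity issue, which each footnote should state.

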5.6 Safety Set with Site 065-S₁ (SS-w-065-S₁)

All randomized patients including patients from site 065-S₁ having received at least one dose of the IMP (either PXL065 or placebo) and considered as-treated will be included in the Safety set with site 065-S₁. The Safety set with site 065-S₁ will be considered as the secondary set for some safety and tolerability analyses. Safety patients are analyzed according to their actual treatment received.

Statistical Analysis Plan

Sponsor Name: Poxel
Sponsor Protocol ID: PXL065-003

5.7 Intent-to-treat Set (ITTS)

The ITTS consists of all as-randomized patients excluding patients from site 065-S , having received at least one dose of the IMP (either PXL065 or placebo). Patients will be assigned to the treatment group as-randomized regardless of the treatment actually received. The ITTS will be considered as the primary set for efficacy analyses.

5.8 Intent-to-treat Set with Site 065-S (ITTS-w-065-S)

The ITTS-w-065-S consists of all as-randomized patients including patients from site 065-S , having received at least one dose of the IMP (either PXL065 or placebo). Patients will be assigned to the treatment group as-randomized regardless of the treatment actually received. The ITTS-w-065-S will be considered for the sensitivity analyses of the primary and secondary efficacy endpoints.

5.9 Per-Protocol Set (PPS)

The PPS consists of all ITTS-w-065-S patients without any important deviation of study procedures some of which include but are not limited to the following:

- Inclusion/Exclusion criteria likely to affect the primary efficacy endpoint satisfied
- Absence of relevant protocol violations with respect to factors likely to affect the primary efficacy endpoint where the nature of protocol violation will be defined before breaking the blind
- Adequate study medication compliance (80-120%) for the overall treatment period where patient has passed Week 12.
- Adequate measurement of the primary variable

The above criteria for the PPS are described in further detail in Section 5.10. Important protocol deviations (PDs) will be identified prior to breaking the blind. All important protocol deviations will be assessed for exclusion from the PPS during the blinded data review meeting (BDRM).

Patients in the PPS will be analyzed based on treatment actually received and actual strata rather than randomized.

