7.6.1.3 Other Analyses for the Primary Endpoint

The same statistical analyses described in Sections 7.6.1.1 and 7.6.1.2 will be repeated for the ITTS-w-065-S .

Additionally, analyses described in Sections 7.6.1.1 and 7.6.1.2 will be repeated without the multivariate imputation on missing Week 36 data for the ITTS and the PPS.

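### SAP 5.9 draws the per-protocol set from the site-inclusive ITT set, so the PPS can contain patients from the compromised site and is not a subset of the primary ITTS

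*SAP*

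**What the plan says.** SAP Section 5 explains that "The analysis populations have been adapted due to data integrity being compromised at site" 065-S. It removes that site's patients from the principal analysis and allows the primary and some secondary endpoints to be analysed with them as a sensitivity analysis. It adds that details of the tables that include the site "will be described in each dedicated part".

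The set definitions follow:

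- Screened Set (5.1) and Randomized Set (5.3): "All patients except patients from site" 065-S. The versions with the site are in 5.2 and 5.4.
- Safety Set (5.5): "All randomized patients except patients from site" 065-S. The version with the site is in 5.6.
- ITTS (5.7), the primary efficacy set: "The ITTS consists of all as-randomized patients excluding patients from site" 065-S. The version with the site, ITTS-w-065-S, is in 5.8.
- PPS (5.9): "The PPS consists of all ITTS-w-065-S patients without any important deviation of study procedures". There is no second version.

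SAP 7.6.1.3 then plans two groups of further analyses of the primary endpoint. For the first, "The same statistical analyses described in Sections 7.6.1.1 and 7.6.1.2 will be repeated for the ITTS-w-065-S". These use multiple imputation. For the second, the same analyses "will be repeated without the multivariate imputation on missing Week 36 data for the ITTS and the PPS".

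Protocol 9.4.3 gives the PPS a single purpose, which is to test the robustness of the primary analysis. Protocol 9.4.3.3 makes it a subset of the protocol's ITTS.

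**The concern.** All four other unsuffixed sets exclude the site. A reader would expect the unsuffixed PPS to do the same, and to be the ITTS with deviators removed. As written it is neither.

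The PPS repeat is the planned robustness check on the primary endpoint. If site patients enter it, a difference between the ITTS and PPS results has two possible sources: the removal of patients with important deviations, and the return of data that the SAP itself distrusts. The reader cannot tell them apart. Agreement between the two results is also harder to read, because the two effects could offset each other.

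**Working it through.** **1. Set membership.** Classify dosed patients by site and by important deviation, and apply 5.7, 5.8 and 5.9 as written.

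| Patient | ITTS-w-065-S | ITTS | PPS as written | PPS if drawn from ITTS |
|---|---|---|---|---|
| Other site, no important deviation | in | in | in | in |
| Other site, important deviation | in | in | out | out |
| Site 065-S, no important deviation | in | out | **in** | out |
| Site 065-S, important deviation | in | out | out | out |

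The third row shows that the PPS as written is not a subset of the ITTS. Drawn from the ITTS, it would be.

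**2. Could another rule remove the third-row patient?** SAP 5.10 to 5.10.6 cover eligibility, prohibited medication, unblinding, allocation errors, compliance and the review process. None of the visible text makes membership of the site a reason for exclusion.

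**3. Effect on the planned comparisons in 7.6.1.3.**

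| Analysis | Site | Multiple imputation |
|---|---|---|
| ITTS, primary | out | yes |
| ITTS, repeat | out | no |
| ITTS-w-065-S | in | yes |
| PPS | possibly in | no |

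The unimputed ITTS matches the PPS on imputation but may differ on the site. ITTS-w-065-S has the same parent population as the PPS but differs on imputation. No unimputed ITTS-w-065-S analysis is planned, so no ITT analysis is sure to match the PPS on both.

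**4. Other places affected.**

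- 7.6.1.3 does not say whether its PPS line includes the site, although Section 5 says such tables will be identified.
- 7.6.2.1 (absolute LFC change) drops the ITTS-w-065-S analysis but keeps the PPS repeat, which could bring site patients back.
- 7.3 summarises PPS-excluding deviations for the ITTS only, so that summary would not reconcile with a site-inclusive PPS. The listing, based on ITTS-w-065-S, would.
- The population table in 7.2 is produced with and without the site and is not at fault.

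**5. Size, as illustration.** The planning inputs are a difference of 30 points and an SD of 30 (SAP 2.3), and 24 evaluable patients per arm (Protocol synopsis).

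The plan's own figures reproduce. The normal approximation gives 22 per arm. Exact t-test power is 89.97% at 22 and 91.25% at 23, so 23 is the exact answer. Dropout: 23/0.8 = 28.75, so 29, and 24/0.8 = 30. In reverse, 120 × 0.8 / 4 = 24.

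Let k of the 24 PPS patients in each arm come from the site, and let d be the treatment difference there. Both are assumptions.

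- Share of the arm for k = 1: 1/24 = 4.2%
- Shift in the PPS difference: (k/24) × (30 − d)
- Standard error of an unadjusted pairwise difference: 30 × √(2/24) = 8.66

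| k per arm | d = 30 | d = 15 | d = 0 |
|---|---|---|---|
| 1 | 0 | 0.625 | 1.25 |
| 4 | 0 | 2.5 | 5.0 |

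**The case against.** The wording may be deliberate. The protocol's ITTS has no site exclusion, so ITTS-w-065-S is the SAP's nearest equivalent, and 5.9 would then keep the protocol's parent population. SAP 5.10.4 refers to both ITT sets when it contrasts them with the PPS, 7.3 lists PPS exclusions for ITTS-w-065-S, and SAP Section 8 records that the PPS description was updated after the blinded data review meeting. Section 5 also permits the site in sensitivity analyses, which is where Protocol 9.5.1 places the PPS repeat. This shows that intent is possible, but the SAP gives no reason, and its change log mentions neither the site nor the parent set. If the site is meant to be in, Section 5 calls for the tables to say so, and 7.6.1.3 does not.

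Site patients may all have been removed already. The review-meeting minutes, the separate deviation document and the note to file are not available, part of the site text is blacked out, and the criteria in 5.9 are not exhaustive. This stands: the documents show only that the PPS can contain site patients.

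The PPS is analysed by treatment received and actual strata, whereas the ITTS is analysed as randomized. The two could therefore differ even after the site is removed. This also stands, but it is a planned per-protocol feature and does not cure the mismatch in population.

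The likely shift is small against its standard error, and the 7.2 tables would let a reader find the number of site patients in the PPS. Both are true. They limit the harm, but the set remains inconsistently defined.

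**Conclusion.** The concern holds. By its definition the PPS can include patients from a site that the SAP removes from the principal analysis, and it is not a subset of the primary efficacy set. The inconsistency is internal to the SAP; the protocol, which has no site exclusion, does not settle it.

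Confidence in the reading of the text is high. Whether any result changes is unknown, because the number of site patients in the PPS is not given. Under the assumed cases the shift runs from nothing to 5 points, and the largest needs four site patients per arm with no treatment effect at the site. The primary ITTS analysis is untouched. This should be fixed because the set's one protocol-stated purpose is to check robustness, and the correction is cheap.

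**What to change.** In SAP 5.9, define the PPS as the patients of the SAP's own ITTS (site excluded) who have no important deviation, in line with 5.1, 5.3, 5.5 and 5.7. Record the change in SAP Section 8 before unblinding. The cost is one line of text and one population flag, and the PPS may be slightly smaller. If no site patient is in the PPS now, its membership does not change.

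If a site-inclusive per-protocol analysis is also wanted:

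- name it PPS-w-065-S;
- compare it with an added unimputed ITTS-w-065-S analysis;
- report the number of site patients per arm;
- base the matching 7.3 deviation summary on the same set.

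This option adds one table and one count.
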